8.5 Post-operative Withdrawal of Enrolled Subjects

A post-operative withdrawal is a Subject who has signed the Informed Consent Document (ICD), has been implanted with a study device, and is later withdrawn from study participation (i.e., withdrawal of consent, revision of any study TKA component, death, etc.). Table 8-9 describes post-operative withdrawal scenarios and the eCRF to be completed. Further description of revision is provided in Section 8.6 Revisions. No data after the date of withdrawal will be included in the clinical analysis.

Table 8-9: Post-operative Withdrawal Scenarios

Example	Action	Follow Up
Subject withdraws consent	 Study site documents Subjects' request for withdrawal from study. Complete Study Completion/Discontinuation eCRF 	Do not continue
Surgeon preference / medical opinion	 Study site documents Surgeons' reason for patient withdrawal from study (should occur under very limited conditions, in order to avoid investigator bias). Complete Study Completion/Discontinuation eCRF 	Do not continue
Death	Complete Adverse Event eCRF Complete Study Completion/Discontinuation eCRF	Do not continue
Revision	See Section 8.6 and Table 8-10 Revision Examples	

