8.4 Discontinuation of Subject Participation

Study participation may be discontinued through screen failure, not receiving the tibial base implant, revision of the femoral and/or tibial component(s), withdrawal of consent, or death. Table 8-8 describes how data will be captured on Subjects that are discontinued prior to receiving the study device while Table 8-9 describes post-op withdrawal scenarios. In all cases, once a subject is enrolled (per Figure 8-1), if they discontinue study participation, the Subject Completion/Discontinuation eCRF must then be completed.

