9.5 Handling of Missing Data

Only actual data will be analyzed; there will be no imputation of missing data.

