11.5 Subject Completion/Discontinuation from the Clinical Investigation

Any Subject is entitled to discontinue/withdraw from this clinical investigation for any reason without obligation and/or prejudice to further treatment. In addition, the Investigator may decide, for reasons of medical prudence, to withdraw a Subject.

The Investigator will clearly document the date and reason(s) for the Subject's discontinuation from this clinical investigation in the Subject Completion/Discontinuation eCRF and submit to DePuy Synthes Products Inc.

Please refer to Section 8.4 Discontinuation of Subject Participation for further details.

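### Withdrawal of an implanted subject on surgeon preference or medical opinion ends data collection, so selective use could bias the responder rate and survivorship

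*Combined protocol and SAP*

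**What the plan says.** Four places deal with how an implanted subject leaves the study.

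- **Section 8.4** says participation "may be discontinued through screen failure, not receiving the tibial base implant, revision of the femoral and/or tibial component(s), withdrawal of consent, or death". It then refers onward: "Table 8-9 describes post-op withdrawal scenarios".
- **Section 8.5, Table 8-9** has a row headed "Surgeon preference / medical opinion". The site documents the surgeon's reason, completes the completion/discontinuation form, and follow-up does not continue. The row adds that this "should occur under very limited conditions, in order to avoid investigator bias".
- **Section 11.5** says "the Investigator may decide, for reasons of medical prudence, to withdraw a Subject", with date and reason sent to the sponsor. It does not mention preference.
- **Section 8.3.4.1** runs adverse event capture to the end of the study, described as study completion or withdrawal of consent. A surgeon-decided withdrawal is neither.

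Two rules then decide what happens to the data. Section 8.5: "No data after the date of withdrawal will be included in the clinical analysis". Section 9.5: "Only actual data will be analyzed; there will be no imputation of missing data".

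The primary FRR is analysed on the Per Protocol set, which requires only one post-operative evaluation at 6 weeks or later (9.6.3). Survivorship is a Kaplan-Meier analysis on the Safety set (9.6, 9.8.4.2). The study is single-arm and unblinded (9.2).

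**The concern.** The person who may end follow-up is unblinded, normally the surgeon who chose and implanted the device, and can see how the knee is doing. When the decision is made, the outcome is lost for good, because nothing recorded afterwards may be used. If the decision is related to a poor result, the loss is informative.

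The primary claim rests on one proportion against a fixed 85% criterion, with no control arm in which similar losses might offset the effect. Section 3.1 intends the data for CE mark registration. The plan itself names investigator bias as the risk of this row, but leaves the conditions for its use undefined and gives no rule for how such subjects count in the analysis.

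**Working it through.** **1. Path from withdrawal to estimate**

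| Timing of surgeon-decided withdrawal | FRR at 1 year | Kaplan-Meier survivorship |
|---|---|---|
| Before any post-operative evaluation | Not in the Per Protocol set | Later revision not counted |
| After a 6-week or 6-month evaluation, before the 1-year KOOS | Eligible for the Per Protocol set, but no 1-year response; out of numerator and denominator | Later revision not counted |
| After the 1-year KOOS | Response already recorded and counted | Later revision not counted |

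These effects are inferred from 8.5, 9.5 and 9.6. No explicit denominator or censoring rule for withdrawn subjects is written. A KOOS or a revision recorded before withdrawal still counts.

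In the second row the subject can stay in the Per Protocol set. Section 9.8.2 asks for reasons for exclusion from the analysis datasets, so that flow diagram need not show this loss.

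**2. Reproducing the plan's sample size**

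Inputs (9.4, 9.7): null rate 0.85, anticipated rate 0.91, one-sided alpha 0.05, power 80%, normal approximation, 15% attrition.

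n = [(1.645·√(0.85·0.15) + 0.842·√(0.91·0.09)) / 0.06]² = 190.5, so 191.

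191 / (1 − 0.15) = 224.7, so 225.

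Both planned figures reproduce. The plan tolerates 225 − 191 = 34 losses.

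**3. Effect of one missing non-responder near the boundary**

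With z = (x/n − 0.85) / √(0.85·0.15/n) and critical value 1.645:

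- 171/191 = 89.5%, z = 1.75: passes.
- 170/191 = 89.0%, z = 1.55: fails.
- 170/190 = 89.5%, z = 1.73: passes.

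This uses the null variance, the form that reproduces 191. If the associated confidence interval is a Wald lower bound, p − 1.645·√(p(1−p)/n), the same step occurs one responder lower: 169/191 gives 0.847 (fails) and 169/190 gives 0.852 (passes).

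**4. Illustration of selective loss**

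Assumptions, none of them from the documents: 191 otherwise evaluable knees, true FRR 85%, and k non-responders (every one a true non-responder) withdrawn before the 1-year KOOS. The chance of declaring success is the binomial probability of reaching the threshold that applies at n = 191 − k.

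| k | n analysed | Responders needed | Expected observed rate, 0.85·191/n | Chance of false success |
|---|---|---|---|---|
| 0 | 191 | 171 | 85.0% | 4.5% |
| 1 | 190 | 170 | 85.4% | 7.0% |
| 3 | 188 | 168 | 86.4% | 14.8% |
| 5 | 186 | 167 | 87.3% | 20.2% |
| 10 | 181 | 162 | 89.7% | 57.7% |

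If withdrawal is unrelated to outcome, the expected rate stays at 85%.

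**5. The same check from the other side**

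174/191 = 91.1% passes. Adding withdrawn knees as non-responders, 174/195 gives z = 1.65 (1.655, just above 1.645) and still passes; 174/196 gives z = 1.48 and fails. At the planned rate, the supportive analysis in the fix would overturn the result at five such knees.

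**The case against.** Much of the case on the other side stands.

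- **The wording conflict is largely editorial.** A reader might infer that 8.4 forbids what Table 8-9 allows. It does not: its next sentence refers to Table 8-9, and its list also omits loss to follow-up, which 8.7 permits. The list is incomplete. The differences among Table 8-9, 11.5 and 8.3.4.1 remain, but they call for alignment.
- **The row is not only about preference.** It also covers medical opinion, and 11.5 speaks of medical prudence. Some uses will be legitimate, for example a subject who can no longer complete questionnaires unaided. Section 4.1 also allows for 1 to 3 additional X-rays, so what remains after surgery is not always routine care.
- **There are safeguards.** The reason is documented, date and reason go to the sponsor, and monitors check that withdrawals are documented and discuss them with the investigator (12.3). These make the decision traceable. They do not recover the outcome or say how the subject counts.
- **KOOS is completed only by the subject.** The surgeon cannot alter a score. The route affects only whether a score exists.
- **The arithmetic is not specific to this route.** Any missing non-responder, whether from consent withdrawal, loss to follow-up or a missed visit, moves 170/191 in the same way. The example is a knife-edge: exactly 170 responders of 191 has probability about 2.5% at a true rate of 85% and 5.9% at 91%.

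This route still differs from other losses in one respect: the decision lies with an unblinded investigator, and the subject may be willing to go on giving data.

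**Conclusion.** The point holds as a possible bias that is cheap to reduce. As written, a surgeon-decided withdrawal before the 1-year KOOS takes the knee out of the FRR, and one at any time in effect censors later revisions. Selective use could move both estimates in the device's favour.

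A reader might go further and infer that the results will be biased, or that one such withdrawal will decide the study. The documents support neither. They give no rate of these withdrawals and no evidence that they are selective, so the size is unknown. The 15% to 20% chance of false success for three to five lost non-responders (1.6% to 2.6% of 191) rests wholly on the stated assumptions: a true rate of 85% and every withdrawn knee a non-responder. It shows only that the margin is narrow compared with the 34 losses the plan already accepts.

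The planned 191 and 225 are unaffected.

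**What to change.** 1. **Reconcile the wording** of 8.4, Table 8-9, 11.5 and 8.3.4.1, so that one rule covers surgeon-decided withdrawal and the end of adverse event capture.
2. **Separate stopping study-specific procedures from ending data collection.** Unless the subject withdraws consent, continue to collect KOOS, adverse events and revision status by the existing PROMs-by-mail plus phone contact. That route now serves subjects unable or unwilling to attend, so extend 8.2.4.1 to these subjects, with the sponsor approval already required. Clinical care stays with the surgeon, as 8.8 already provides.
3. **Include those data in the analysis** by amending the exclusion in 8.5.
4. **List each surgeon-decided stop** with reason and date in the 9.8.2 disposition, including subjects who stay in the Per Protocol set. The information is already collected.
5. **Add a supportive FRR** that counts such knees without a 1-year KOOS as non-responders. The primary analysis does not change.

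Cost: a few more contacts per site, small edits to sections 8, 9 and 11, and a supportive rate that may be slightly less favourable.

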8.6 Revisions

A "revision" is defined as a surgical procedure of the affected knee where one or more of the TKA components (metal femoral component and/or metal tibial base, polyethylene insert, or patella polyethylene resurfacing component) are removed. Should it be necessary for the Subject to undergo a revision of any ATTUNE Cementless Femoral and/or Tibial Base component between the time of enrolment and completion of the study data acquisition, the Subject is to be withdrawn from study participation. Thus, both an Adverse Event (AE) eCRF and the Subject Completion/Discontinuation eCRF must be completed (see Table 8-9). Note that if a tibial insert is exchanged and/or a resurfaced patella is revised, but both the femoral and tibial base components remain, then an AE eCRF must be completed, but the subject is not to be withdrawn from the study.

A "re-operation" is defined as any surgical procedure of the affected knee in which none of the TKA components are removed. Examples include irrigation & debridement without tibial insert exchange or the resurfacing of a previously unresurfaced patella. These subjects are not to be withdrawn. An Adverse Event (AE) eCRF must be completed.

Table 8-10: Revision and Reoperation Examples

Example	Actions	Follow Up
Removal / revision of metal Tibial Base and/or Femoral component	 Complete Adverse Event eCRF Complete Revision/Reoperation eCRF Complete Study Completion/Discontinuation eCRF 	Do not continue
Tibial Insert polyethylene exchange	Complete Adverse Event eCRF Complete Revision/Reoperation eCRF	Continue
Revision of a previously resurfaced patella	 Complete Adverse Event eCRF Complete Revision/Reoperation eCRF 	Continue
Resurfacing of a previously unresurfaced patella in combination with a Tibial polyethylene exchange	 Complete Adverse Event eCRF Complete Revision/Reoperation eCRF 	Continue

8.7 Lost to Follow-up

Although follow-up compliance is essential to study quality, some Subjects may not be able to return for follow-up evaluations. Sites should make every effort to ensure complete follow-up including phone calls and/or written requests to a Subject. If these approaches are not successful, then the site may document a Subject as lost-to-follow-up on the Subject Completion/Discontinuation eCRF. Contact attempts (minimum of 3 attempts) should be documented in the Subject's medical notes.

8.8 Medical Care Following Study End

In the event that a study subject is withdrawn from the study for any reason, their follow-up care will continue per their surgeon's standard of care.

9 STATISTICAL METHODOLOGY

This section describes the statistical methods for the study design and planned analysis of study data.

9.1 Study Design

This is a prospective, multi-center, non-randomized, single arm observational study. A minimum of 600 subjects will be enrolled at a maximum of 25 sites in the United States. Two (2) implant configurations will be studied: 300 CR FB knees (CR or MS Tibial Inserts) and 300 PS FB knees (PS Tibial Inserts) and up to 300 Cementless Patellae (if available in United States market during the clinical study).

9.2 Treatment Assignment

This is a non-randomized, non-comparative, unblinded study; all subjects will receive an ATTUNE® Cementless FB Tibial Base. Each surgeon will use their standard of care configuration for enrolled subjects. This includes either the CR FB (CR or MS Tibial Inserts), PS FB, or both. In addition, surgeons will select to resurface the patella with the ATTUNE Cemented Patella or the ATTUNE Cementless Patella once available or leave the patella unresurfaced.

9.3 Interval Windows

The pre-operative assessment is to be done between 180 days prior to the procedure up to day -1 (day zero defined as the day of the index procedure for this study); radiographs for this study may be from 180 days prior to day -1 (or longer if the PI determines they are acceptable for surgical planning). The required window intervals are defined as follows for analysis purposes:

Table 9-1: Interval Windows

Required* Follow-up Intervals (days)								
Pre-op**	Day 0	6 Week	6 Months	1 Year	2 Year	3 Year Contact	4 Year Contact	5 Year
-180 to -1d	0 (Defined as the Day of TKA)	1-90	91-303	304-669	670-1033	1034-1398	1399-1763	1764- 2044
Preferred* F	Preferred* Follow-up Intervals (days)							
Pre-op**	Day 0	6 Week	6 Months	1 Year	2 Year	3 Year Contact	4 Year Contact	5 Year
-90 to -1d								

^{*} Although these are the windows for analysis purposes, narrower "preferred" interval windows have also been included in this protocol

Multiple visits within these defined windows for a single subject may occasionally occur. If this occurs, then for both the pre-op interval the visit closest to the date of surgery will be considered the study visit. Individual pre-op data (i.e. radiographs, PROMs, etc.) may be collected at different pre-op visits and each type of data will be considered separately when considering multiple visits. For post-op intervals the later of the visits will be considered the study visit for analysis purposes.

DSJ_2019_05, Rev D (FINAL) 24 August 2022 DePuy Synthes Products, Inc. - Confidential

^{**} Pre-operative radiographs may be in the window -180 to -1 days (or longer if the PI determines they are acceptable for surgical planning)

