8.2.4 Post-operative Management

Immediate post-operative management including physical therapy protocol is at the discretion of the Surgeon and support staff and should follow each Surgeon's standard of care. Rehabilitation programs are often individualized.

The methods of data collection and follow-up windows have been selected to achieve the primary objective of evaluating functional responder rates from baseline to one year as measured from the KOOS questionnaire, as well as providing further data to include survivorship and performance measures out to five years. Every effort should be made to schedule the post-operative follow-up within these windows to enhance follow-up compliance. While required interval windows have been designed to be continuous to improve follow-up compliance and accommodate various standards of care across sites, this study includes preferred windows as well to increase the consistency with respect to the timing of data collection, since function is changing with time, particularly in the early recovery phase.

All follow-up visits will be conducted according to the Time and Events Table (Table 1-1), and applicable eCRFs must be submitted to DePuy Synthes Products Inc. Data collected during the post-operative management of the Subject is listed in Table 8-1.

8.2.4.1 Postoperative Data Collection Methods:

A postoperative follow-up is to be done ONLY by a clinic visit at the 6 week, 6 month, 1 year, 2 year and 5 year follow-up windows. The phone contact visit is to be done only at postoperative years 3 and 4:

The definition of a **Clinic visit** as defined by this protocol is either of the below:

- The Preferred In Clinic Method: Subject is seen in clinic, receives an assessment of the study knee including study required radiographs, the Subject completes the source document PROMs and the required data is submitted to the Sponsor as per protocol (See Time and Events Table 1-1).

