- An Alternative PROMS by Mail Method + Phone Contact* (postoperative follow-up only): This method is to be done in the event the Subject is either unable or unwilling to be seen in the clinic office and agrees to complete and return the study required PROMs by mail AND attend a follow-up phone contact visit*. Upon completion of both methods of data collection (in the same interval window), an alternative clinic visit will be considered completed. This type of visit allows for the surgeon portion of the AKS and radiographs to be optional. The details associated with administration of PROMs are described in Section 8.2.1 and apply for this method of data collection A sample cover letter, Contact Form, and Phone Script are provided in Exhibit F.

The definition of a *Phone Contact visit is defined as:

A telephone call with the Study Subject (See Time and Events Table 1-1). In order to optimize the accuracy of survivorship data, enable timely capture of AEs and maximize the chance of good long- term follow-up, contact will be made with each Subject at 3 and 4 years post-operatively. These telephone contact visits will occur in between the 2yr and 5yr clinic visits and will ideally occur within the preferred window. No PROMs are to be completed.

Phone Contact visits will take the form of a telephone call where a member of the study team, typically a Research Coordinator, speaks with the study Subject. The topics to be covered and information to be collected during the call will include: confirmation of the Subject's contact information; assessment of whether there has been a revision or any adverse events to the Subject's implanted knee for the study; reminder to the Subject of their next scheduled visit and the importance of their continued study participation. As an alternative approach if in keeping with sites' standard of care, the data collected via a phone contact visit can be collected face to face (in clinic or virtual) or via mail in lieu of being done over the phone.

Note: If a full clinic visit data set is collected at the phone contact intervals (3 & 4 yrs postoperatively), the site will only be compensated for a phone contact type visit.

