9.8.4.1 Primary Endpoint and Associated Hypotheses

The primary endpoint is the Functional Responder Rate (FRR) at 1 year. A Functional Responder is defined as:

- A subject that shows at least 20% improvement from baseline and at least a 10-point improvement from baseline in at least 2 of the following categories:
 - o KOOS (ADL)
 - o KOOS (Pain)
 - o KOOS (Quality of Life)

Functional Responder rates are expected to be between 91%-94%. The objective performance criteria for study success is 85%.

$$H_0$$
: FRR $\leq 85\%$

$$H_A: FRR > 85\%$$

The primary endpoint will be performed on the first 225 tibia implanted with the ATTUNE Cementless FB tray (primary and revision procedures, CR FB and PS FB combined) and will be analyzed when these patients have passed the 1 year preferred post-op window (395 days). This analysis will be done on the Per Protocol (PP) population. Study success will be determined using the primary TKA (CR FB and PS FB combined) analysis group.

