9.8.4.2 Secondary Endpoints and Associated Hypotheses

The secondary endpoints in this study are:

- Type and frequency of Adverse Events and Device Deficiencies.
 - Functional responder rates with an objective performance criteria (OPC) of 85% as measured by the KOOS questionnaire for all subjects (CR FB and PS FB combined) at the 1 year timepoint.
- The change from preoperative baseline to the 6 week, 6 month, 1 year, 2 year and 5 year timepoints in functional outcomes and quality of life assessments, as measured using additional patient reported outcomes measures (PROMS):
 - o AKS 2011
 - KOOS (all subscores)
 - FJS-12 (changes post-operatively only)
 - o *EQ-5D-5L*
- Implant survivorship of the ATTUNE Cementless FB Tibial Base using Kaplan-Meier survival analysis at 1, 2 and 5 year timepoints.
- Investigator-conducted radiographic analysis of the tibial and patellar components at 6 weeks/6 months, 1, 2 and 5 years after surgery.

All secondary endpoint analyses may be conducted after all patients have passed the recommended study window (ex. with a 2-year follow-up analysis conducted after all subjects have passed 790 days post-op). All analyses at these time points will be conducted again with final data, along with endpoints which have a 5-year follow-up time point, with locked data at the close of the study.

A Kaplan-Meier survivorship model will be used to estimate survivorship rates (where a revision is defined in Section 8.6) along with a two-sided, log-log based 95% confidence intervals; this analysis will be conducted on the Safety analysis set.

The types and frequencies of adverse events that occur throughout the study will be tabulated by MedDRA system organ class (SOC) and preferred term (PT) for all Subjects in the Safety analysis set. The proportion of Subjects experiencing each complication (PT within SOC) will be presented, and a 95% confidence interval will be estimated with the binomial exact method.

All other specified secondary endpoints will be presented with statistical summaries at each respective time point; these secondary endpoint analyses will be carried out with all data on subjects in the Per Protocol analysis set.

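### The later-visit rule in section 9.3 can replace an on-target 1-year KOOS with one taken as late as day 669, and the primary endpoint is not exempt

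*Combined protocol and SAP*

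**What the plan says.** Section 9.3 makes the required windows the analysis windows. In Table 1-1 and Table 9-1 the required 1-year window is days 304 to 669. Table 1-1 gives the preferred 1-year window as days 335 to 395.

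Section 9.3 foresees repeat visits: "Multiple visits within these defined windows for a single subject may occasionally occur". Before surgery it takes the assessment nearest to the operation and adds that "each type of data will be considered separately when considering multiple visits". After surgery the rule is different: "For post-op intervals the later of the visits will be considered the study visit for analysis purposes".

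Section 8.2.4 says the preferred windows were added "to increase the consistency with respect to the timing of data collection, since function is changing with time". The sentence goes on to stress early recovery.

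Section 9.8.4.1 defines the 1-year Functional Responder Rate and lets the primary analysis run once the first 225 knees have passed day 395. That is a trigger. It is neither a data cut-off nor a rule for choosing among visits. Section 9.8.4.2 lists a 1-year responder rate for all subjects as a secondary endpoint and says of the secondary analyses: "All analyses at these time points will be conducted again with final data". Section 9.4 states that the primary test is the study's only hypothesis.

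**The concern.** A selection rule is there to decide which value counts when a knee has more than one. Whenever an on-target KOOS is followed by another in the same window, this rule picks the value further from 1 year. A 2-year visit held just before day 670 would be counted as the 1-year visit and would override the real one.

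Two things are at stake. The endpoint of the only hypothesis test is meant to describe function at 1 year, yet for some knees it may describe function at up to about 22 months. Also, because the window stays open long after the day-395 trigger, one knee can be a 1-year responder in the primary analysis and a non-responder in the all-subject analysis, or the reverse. The plan does not say that the primary test itself is re-run.

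**Working it through.** **Inputs.** Required 1-year window 304 to 669 and preferred window 335 to 395 (Table 1-1); later-visit rule (9.3); trigger at day 395 (9.8.4.1); 85% criterion, 91% assumed rate, 191 evaluable and 225 enrolled knees, one-sided test at 0.05 by normal approximation (9.4, 9.7).

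**1. The plan's sample size.** n = [(1.645·√(0.85·0.15) + 0.842·√(0.91·0.09)) / 0.06]² = 190.5, so 191; power at 191 is 80.1%. With 15% attrition, 191/0.85 = 224.7, so 225. Both figures reproduce, and neither depends on visit selection.

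**2. Window geometry.**
- Target day: (335 + 395)/2 = 365.
- Required window: 669 − 304 + 1 = 366 days.
- Split: 31 days before the preferred window (304 to 334), 61 in it (335 to 395) and 274 after it (396 to 669); 31 + 61 + 274 = 366.
- Share after the preferred window: 274/366 = 75%.

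**3. Current rule.** Latest value that can be used: 669 − 365 = 304 days past target. The gap between the displaced and the replacing KOOS can be larger: from day 335 it reaches 669 − 335 = 334 days. After the trigger, a replacement is possible on any of 274 days.

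**4. Effect of the data cut.** No visit cut-off is stated. Knees implanted early among the 225 can contribute values up to day 669. The last ones implanted may have little beyond day 395 when the analysis runs. How far a value can drift therefore depends partly on implantation order.

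**5. Rule proposed under the fix** (preferred window first, then closest to day 365, ties to the earlier).

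| Knee | Maximum drift from day 365 | Can the value change after day 395? |
|---|---|---|
| (a) KOOS in days 335 to 395 | 395 − 365 = 30 days | No |
| (b) Only KOOS by day 395 is on day d, 304 to 334 | 365 − 304 = 61 days | Only if a later day e satisfies e − 365 < 365 − d, i.e. e < 730 − d. For d = 304, days 396 to 425; for d = 334, none |
| (c) First KOOS after day 395 | 669 − 365 = 304 days | No; every later day is further from 365 |

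**6. How much room the test has.** With 191 knees, z = (x/191 − 0.85)/√(0.85·0.15/191). For x = 171, z = 1.75; for x = 170, z = 1.55. Success against 1.645 thus needs 171 responders, and 0.91 × 191 = 173.8 are expected, a margin of about three knees.

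As an illustration only, assume that a share f of knees has a second KOOS and that the responder rate among them shifts by a net d, so the overall rate is 0.91 + f·d. Neither figure is in the documents. For f = 2% and d = ±10 points the rate is 90.8% to 91.2% and power 77% to 83%. For f = 10% and the same d, the rate is 90.0% to 92.0% and power 63% to 92%. This shows sensitivity and does not predict an effect.

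**The case against.** The strongest reply is that this will seldom matter. KOOS is scheduled once in the 1-year interval, and a second value needs a repeated 1-year visit, a 6-month visit after day 303 or a 2-year visit before day 670. That last visit would be early against both 2-year windows, since both open on day 670. The 304 days is a ceiling and not an expected drift. Section 8.2.4 puts its emphasis on early recovery, so change after 1 year may be modest, and it explains that the required windows were made continuous for compliance and local practice. The later-visit rule is also right in one ordering: a late 6-month visit on day 310 followed by a 1-year visit on day 365 yields the on-target value. Finally, the rule is prespecified and takes no account of KOOS results, and changing it mid-study has a credibility cost.

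Much of this stands as a limit on weight. The frequency is unknown and no bias is shown. It does not rescue the rule, because a closest-to-target rule gives the same good answer in the day-310 example and a better one in the reverse ordering. Analysing on wide windows for compliance does not require preferring the latest visit within them. A sensitivity analysis alone would show whether timing matters, but would leave the primary value poorly chosen.

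**Conclusion.** The concern holds and should be corrected. As written, the plan discards an on-target 1-year KOOS whenever a later one falls in days 304 to 669, and the primary endpoint is not exempt.

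The established size concerns timing only: up to 304 days past day 365, with 274 days of possible replacement after the trigger. This takes day 365, the midpoint of the preferred window, as the 1-year target. No effect on the responder rate is established, because the documents give no double-visit rate. The sample size is unaffected.

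A smaller point is wording. Section 9.3 states separate handling by data type only for pre-operative data, so read literally a later post-operative visit without a KOOS could displace one that has it. Section 8.2.4.1 makes PROMs part of a completed clinic visit, including the mail-and-phone alternative ("Upon completion of both methods of data collection (in the same interval window), an alternative clinic visit will be considered completed"), so a clarification is enough.

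**What to change.** Replace the post-operative sentence in section 9.3 so that, for each data type separately:

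1. the assessment used is the one in the preferred window closest to its midpoint (day 365 for 1 year);
2. if there is none, it is the assessment in the required window closest to that day;
3. ties go to the earlier assessment.

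Add a sensitivity analysis of the primary endpoint limited to KOOS from days 335 to 395. State in the plan that knees without a preferred-window KOOS may still be off target, or may change between data cuts (cases b and c in the table).

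The cost is a few sentences, minor programming and one sensitivity table resting on fewer knees. Sample size and data collection do not change. Section 9.2 says "This is a non-randomized, non-comparative, unblinded study", and the Table 8.2 note in section 8.2.3 provides for subjects enrolled before the current amendment. The change therefore also needs a dated justification that states what outcome data had been seen when the rule was changed.
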